### In conventional group:

1- A power point presentation will be provided to the children. (One visit)

### In non-conventional group:

1- Children will be subjected to an interactive learning approach that includes: (Four visits)

-Brain-based learning strategies using storytelling and hands-on activities.

-An online game-based learning platform (Kahoot).

(It can be accessed via a web browser or the Kahoot app).

2-Mothers will be subjected to an oral health education lecture.

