#### **Objectives:**

-To measure the oral hygiene status of preschool children using simplified oral hygiene index.

-To assess mothers' oral hygiene knowledge, attitudes, and practices towards their children using an online questionnaire.

-To measure the impact of conventional oral health education on the oral hygiene status of preschool children and mothers' knowledge, attitudes and practices.

-To measure the impact of non-conventional oral health education on the oral hygiene status of preschool children and mothers' knowledge, attitudes and practices.

-To compare the effect of conventional versus non-conventional oral health education on the oral hygiene status of preschool children and on mothers' oral hygiene knowledge, attitudes, and practices towards their children.

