#### **Inclusion criteria:**

-Children aged 5-6 years who are registered in the respective academic year at kindergarten

schools in Al-Ahsa.

-Mothers of preschool children who agree to participate and provide consent.

-Children and mothers who can attend all educational sessions.

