#### The oral health education program will be delivered by:

Specialized kindergarten teachers.

Teachers will undergo through a special, well-structured program for preparation, training and calibration.

For children, they will receive the program during regular school hours on weekdays.

**For mothers**, depending on what they prefer, the lecture will either be arranged in person or virtually via the Zoom online platform.

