### **Non-conventional Oral Health Education**

1.First Visit: Introduction to the importance of oral hygiene through visual storytelling, depicting a child who experiences dental pain due to poor oral hygiene. And game-based session using puzzle and Kahoot app for question-and-answer activities related to oral hygiene.

2.Second Visit: Explanation of the process of plaque accumulation and hands-on activity where children practice brushing plaque off a paper character to simulate good oral hygiene practices. And game-based session using Kahoot for question-and-answer activities related to plaque accumulation

3. Third Visit: Explanation of the importance and components of the mouth and the right way for brushing teeth including activity on a jaw model to apply the correct brushing technique. And game-based session using Kahoot for question-and-answer activities related to importance and components of the mouth.

4.Fourth Visit: Oral hygiene instruction, how to keep our teeth healthy and reinforcement of preventive measures such as dental visits. And game-based session using memory matching game and Kahoot app for question-and-answer activities related to healthy mouth.

Then, over a period of 3 months, this game will be played online from home in a competitive and group setting once a week.

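### The protocol contradicts itself on whether conventional-arm mothers receive any education; as the arms are listed, the maternal outcomes compare a lecture with no lecture

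*Protocol*

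**What the plan says.** **Arm content.** Under *In conventional group* there is a single numbered item: "A power point presentation will be provided to the children. (One visit"). Nothing is listed for mothers. Under *In non-conventional group*, item 1 reads "Children will be subjected to an interactive learning approach that includes: (Four visits") and item 2 reads "Mothers will be subjected to an oral health education lecture". *Non-conventional Oral Health Education* then adds a home component after the four visits: "over a period of 3 months, this game will be played online from home in a competitive and group setting once a week".

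**Text that names no arm.** The section on who delivers the programme says of mothers that, "depending on what they prefer, the lecture will either be arranged in person or virtually via the Zoom online platform". The inclusion criteria ask for "Children and mothers who can attend all educational sessions".

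**What is to be tested.** One objective is "To measure the impact of conventional oral health education on the oral hygiene status of preschool children and mothers' knowledge, attitudes and practices"; a parallel objective covers non-conventional education, and a further one compares the two. *Hypothesis* and *Null Hypothesis* state the comparison for the child's oral hygiene and for the three maternal outcomes together. *Data analysis* names four dependent variables (child oral hygiene status; mothers' knowledge, attitudes and practices) and makes the type of education the independent variable.

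**The concern.** What each arm receives belongs in the protocol, and no later analysis can settle it. Staff who follow the arm lists would teach mothers in one arm only. The maternal results would then contrast some direct education with none, while the objectives describe them as conventional against non-conventional education. A reader of the results could credit storytelling and games for an effect that a lecture to mothers produced.

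The child outcome is exposed as well. The protocol's Introduction treats lack of awareness among parents and other guardians as a barrier to prevention. By that reasoning, a lecture to mothers is a plausible route to a better plaque score.

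**Working it through.** The point turns on what the sections say, so they are set side by side first. A short calculation then shows how easily a lecture alone could produce a significant maternal result.

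**1. Does any section give conventional-arm mothers education?**

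| Section | Names an arm? | Education for mothers |
|---|---|---|
| In conventional group | Conventional | None listed |
| In non-conventional group | Non-conventional | Lecture |
| The oral health education program will be delivered by | No | Lecture, in person or by Zoom |
| Inclusion criteria | No | Mothers able to attend the sessions |
| Objectives; Hypothesis; Null Hypothesis | Both | Maternal outcomes compared between types of education |

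No section assigns the lecture to the conventional arm, and none withholds it in so many words. The undertaking under *Exclusion criteria* that nobody is deprived of learning covers children, not mothers.

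**2. How many outcomes are affected?** Of the four dependent variables under *Data analysis*, knowledge, attitudes and practices are maternal: 3 of 4. The fourth, the child's score, is affected indirectly.

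**3. What differs between the arms as listed?** Conventional: 1 visit to the children. Non-conventional: 4 visits, a weekly home game over 3 months (about 3 × 4 = 12 occasions, taking a month as four weeks), and the mothers' lecture. The packages therefore differ in teaching method, in amount of contact and in whether the mother is taught.

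**4. Could the lecture alone produce a significant maternal result?** The protocol gives no effect size or standard deviation, so this is an illustration under assumptions:
- 394 pairs per arm, which is the protocol's 788 before the dropout allowance, divided by 2;
- a two-sided test at 0.05 (the protocol gives 0.05 but not the sidedness);
- individual-level analysis with clustering by class ignored;
- no effect of the children's teaching method on mothers;
- a lecture effect of d standard deviations on a maternal score.

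Probability of significance ≈ Φ(d × √(394/2) − 1.96), with √197 = 14.04.

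| d | d × 14.04 − 1.96 | Probability |
|---|---|---|
| 0.1 | −0.56 | 0.29 |
| 0.2 | 0.85 | 0.80 |
| 0.3 | 2.25 | 0.99 |
| 0.5 | 5.06 | 1.00 |

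A modest lecture effect would usually give a significant maternal difference even if the children's method did nothing for mothers. Classes are the units allocated, so an analysis that allowed for clustering would give lower probabilities. The problem of attribution would be the same.

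**5. What follows under each reading?**
- *Lecture in one arm only:* the maternal contrast is lecture versus no lecture, and the child contrast is package versus package.
- *Same lecture in both arms:* the direct maternal education is equal, so the maternal outcomes test only what reaches the mother through the child's programme.

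Neither reading matches the objective of measuring what conventional and non-conventional education each do for mothers.

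**The case against.** The strongest reply is that a lecture in both arms was probably intended. The delivery section comes before the arm descriptions, speaks of the programme as a whole, and pairs children (who are taught in both arms) with mothers. The inclusion criterion on attendance likewise names no arm. The conventional list holds only an item numbered 1, so a second item may have been omitted. This stands as far as it goes: a reader might infer that conventional-arm mothers certainly receive nothing, and the document does not support that certainty. It does not remove the contradiction, because the only arm-by-arm list still places the lecture in one arm.

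A second reply is that the trial compares programmes, and a comparison of whole packages under randomisation is valid. This also stands. It would be too strong to say that the trial cannot compare the conventional with the non-conventional programme; what is lost is attribution to the teaching method.

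A third reply is that four visits against one is deliberate. The Introduction stresses repetition and reinforcement, and the extra visits and weekly play are part of the programme. Unequal contact is therefore not an error in itself. It matters only for how the result is described.

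A reader might also infer that the arms are re-examined at different times. *Measurements* sets the same interval for both groups, so the document does not support that as a finding.

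**Conclusion.** The concern holds as an internal contradiction with consequences for interpretation. As the arms are listed, three of the four dependent variables compare a mothers' lecture with no direct maternal education, and the child's score may carry part of the lecture's effect. A difference could be reported validly as an effect of the whole package, but not as evidence for interactive over conventional teaching.

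The contradiction and the count of outcomes rest on the text alone. The probabilities rest on the stated assumptions and only illustrate the risk. No sample-size figure changes. The document does not establish what conventional-arm mothers will in fact receive, and it does not say that a result would be presented as superiority of games alone. The matter should be settled before the programme starts, since it decides what the trial can conclude.

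**What to change.** Reconcile *Inclusion criteria*, the section on who delivers the programme, *In conventional group* and *In non-conventional group*, so that the protocol says plainly what mothers in each arm receive. The choice is the investigators'; the rest of the text must then follow it.

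- **If both arms' mothers get the lecture:** list it under *In conventional group*, and state that the maternal outcomes then test only the indirect effect of the children's programme.
- **If only one arm's mothers get it:** name that arm in the delivery section and in the attendance criterion. Reword the aim, objectives, hypothesis and null hypothesis so that the maternal contrast is lecture versus no lecture. Describe both the maternal and the child results as effects of the whole package, including its greater contact time, and not of the teaching method.

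The second option costs only wording. The first also means inviting the other arm's mothers to a lecture for which the protocol already allows virtual delivery. No change to the examination schedule is needed for this point.

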### **Non-conventional Oral Health Education**

1.First Visit: Introduction to the importance of oral hygiene through visual storytelling, depicting a child who experiences dental pain due to poor oral hygiene. And game-based session using puzzle and Kahoot app for question-and-answer activities related to oral hygiene.

2.Second Visit: Explanation of the process of plaque accumulation and hands-on activity where children practice brushing plaque off a paper character to simulate good oral hygiene practices. And game-based session using Kahoot for question-and-answer activities related to plaque accumulation

3. Third Visit: Explanation of the importance and components of the mouth and the right way for brushing teeth including activity on a jaw model to apply the correct brushing technique. And game-based session using Kahoot for question-and-answer activities related to importance and components of the mouth.

4.Fourth Visit: Oral hygiene instruction, how to keep our teeth healthy and reinforcement of preventive measures such as dental visits. And game-based session using memory matching game and Kahoot app for question-and-answer activities related to healthy mouth.

Then, over a period of 3 months, this game will be played online from home in a competitive and group setting once a week.

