
changes (Aljafari, ElKarmi et al. 2022). Health promotion is provided to help individuals manage and enhance their health. Besides, Oral Health Education (OHE) is an important element of oral health promotion and a necessary component of oral health care. Through educational approaches, information is given to increase oral health awareness in order to adopt a healthy lifestyle, improved attitudes, and desired behaviors (Gurav, Shetty et al. 2022). However, waiting to educate children about oral health until they seek dental care is occasionally too late, especially in nations and communities where people only visit the dentist when experiencing pain. Accordingly, it is important to provide oral health education in nonclinical settings (Aljafari, ElKarmi et al. 2022). Oral health education encompasses several strategies, such as public awareness campaigns, informative presentations in primary schools, the use of oral health films, and establishing a complete and reinforced course that is incorporated into the school curriculum (Gurav, Shetty et al. 2022). The implementation of OHE programs in schools is critical for achieving adaptive changes and improving oral wellbeing. School plays an important part in a child's development, enabling them to proceed towards becoming successful (K, Deshpande et al. 2022). Additionally, school years are a child's physical and mental formative years, shaping them into potential adults. The health behaviors that are developed during this phase will persist until adulthood, old age, and maybe into the next generation (Malik, Sabharwal et al. 2017). Also, children have a rapid capacity for assimilating new information. Furthermore, the acquisition of habits at an earlier stage has a more enduring influence (Sharma, Saxena et al. 2021, Gurav, Shetty et al. 2022). Fortunately, school is one of the most accessible avenues for reaching out to children and their families and considered an ideal platform for providing OHE. They may reach over one billion children worldwide, which supply an excellent opportunity for supporting children to improve their healthrelated behaviors (PEREIRA and MATHEW 2020, Gurav, Shetty et al. 2022). Dental health education in schools is conducted through a variety of methods, from simple educational presentations to technology-enabled multimedia programs that include strategies designed to support behavioral and psychological changes. The efficacy of oral health education in schools is based on the extent to which the acquired health behaviors are retained. In order to have a longlasting effect, it is essential to use repetition and reinforcement approaches in health education (PEREIRA and MATHEW 2020). Studies show that the use of conventional OHE alone does not provide sufficient outcomes for modifying oral health behavior and attitude (K, Deshpande et al. 2022). Furthermore, research has revealed that these particular programs have little impact on oral

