# **Hypothesis**

Non-conventional oral health education can improve the oral hygiene status of preschool children, and mothers' oral hygiene knowledge, attitudes, and practices towards their children more than the conventional programs.

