#### **Measurements:**

**1- Children's plaque index** will be measured using simplified oral hygiene index (S-OHI). The plaque scores will be recorded according to the (S-OHI) to assess oral hygiene status for children. The oral examination will be performed using a sterilized disposable examination kit, including a mouth mirror and explorer, in a separate classroom with each student seated on a chair under optimum artificial light.

The examiners will perform an oral examination for children in both groups and record their plaque score before the intervention and after 3 months of intervention. Oral examination will be conducted in the morning hours before the school meal. Children will not be informed about the day of examination to prevent **Hawthorne effect**. **Hawthorne Effect:** It is a psychological phenomenon that occurs when individuals modify their behavior or performance in response to the awareness of being observed.

**2-Mothers' oral hygiene knowledge, attitudes, and practices towards their children**, using a questionnaire. Paper questionnaire will be submitted before the intervention and after 3 months of intervention.

3-Demographic information, parents' socioeconomic condition, dietary habits and oral hygiene performance to reduce confounding factors, using a self-administered questionnaire to complete at home and return to the researchers before conducting the study.

(Accounting for the cultural sensitivity self-administered parental questionnaire will be used. Before conducting the study, the validity and practicality of the questionnaire will be tested.) Evaluations of children's oral hygiene status and mothers' knowledge, attitude and practices toward their children will be recorded before the intervention and after 3 months of intervention for the two groups.

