#### By the end of implementing oral health education, we will compare:

The children's oral hygiene status and mothers' knowledge, attitude and practice toward their children between the conventional and non-conventional group.

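### The hypotheses contrast types of education, but the arms differ in amount of contact as well as format, so a difference belongs to the whole programme and not to the interactive method

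*Protocol*

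**What the plan says.** The Protocol's aim is to evaluate conventional against non-conventional oral health education. The Hypothesis section begins "Non-conventional oral health education can improve the oral hygiene status of preschool children" and goes on to claim a larger improvement than with conventional programmes. The Null Hypothesis is the matching statement of no difference between the two kinds of education.

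The arms are defined as follows.

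- Conventional (section In conventional group): "A power point presentation will be provided to the children. (One visit"). No home activity or later reinforcement is described for these children.
- Non-conventional (section In non-conventional group): "Children will be subjected to an interactive learning approach that includes: (Four visits"). The detailed description then adds that "over a period of 3 months, this game will be played online from home in a competitive and group setting once a week".
- Mothers: an educational lecture is listed under the non-conventional arm only. The section on who delivers the programme describes how mothers' lectures are arranged without naming an arm.

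On timing, the Measurements section has the examiners "record their plaque score before the intervention and after 3 months of intervention", and the mothers' questionnaire follows the same two time points. The between-arm comparison is introduced with "By the end of implementing oral health education, we will compare". No later measurement is described.

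**The concern.** The Introduction's rationale is about method: it argues that interactive, game-based learning works better than conventional teaching. The hypotheses carry that framing forward. The design, however, changes two things together: how the children are taught, and how often.

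The Introduction supplies the rival explanation itself. For a lasting effect, it says, "it is essential to use repetition and reinforcement approaches in health education". Only one arm receives repetition. A difference could arise from the format, from the extra contact, or from both. Randomisation does not help, because the amount of contact is part of what is assigned.

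What is at stake is the conclusion. As the hypothesis is framed, a significant result would be credited to the non-conventional type of education. A kindergarten that replaced its slide talk with a single game session could not rely on that result. For the mothers' outcomes there is the further question of whether one group had a lecture and the other did not.

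**Working it through.** The Protocol gives no total of contacts per arm, so there is no stated figure to reproduce. The count below uses its own entries.

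**Step 1. Planned child contacts before the outcome**

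| Input | Value | Source (Protocol) |
|---|---|---|
| Conventional visits | 1 | In conventional group |
| Non-conventional visits | 4 | In non-conventional group |
| Home games | 1 per week for 3 months | Non-conventional Oral Health Education |

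Three months is 84 to 91 days, and 84/7 = 12, 91/7 = 13, so 12 to 13 games.

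- School visits only: 4 versus 1, ratio 4:1.
- All planned contacts: 4 + 12 = 16 to 4 + 13 = 17, versus 1, ratio 16:1 to 17:1.

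**Step 2. Sensitivity to uptake of home play**

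Contacts = 4 + (share played) × (12 to 13). The Protocol gives no expected uptake, so the shares are assumptions.

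| Share of games played | Non-conventional contacts | Conventional |
|---|---|---|
| 0 | 4 | 1 |
| 0.5 | 10 to 10.5 | 1 |
| 1 | 16 to 17 | 1 |

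Amount differs between the arms at every share, including zero. Session lengths are not stated, so the ratio in contact time cannot be computed.

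**Step 3. Can the analysis separate format from amount?**

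There are two arms. One combines slides with one contact; the other combines interactive teaching with many. No arm has slides with many contacts or interactive teaching with one. The difference between the arms is therefore the sum of a format effect, an amount effect and any interaction (plus a lecture effect if only one group of mothers is lectured). One contrast cannot identify these parts. The t-tests and Chi-squared tests under Data analysis estimate the total only, and no analysis plan could recover the parts from these data without further assumptions.

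**Step 4. When the outcome falls**

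The start of the 3 months is not stated. Take 3 months as 13 weeks and let the four visits span *v* weeks (not given), with weekly play following them. Play ends at week *v* + 13.

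| 3 months counted from | Examination | Position relative to end of weekly play |
|---|---|---|
| Last school visit | week *v* + 13 | 0 weeks: coincides |
| First school visit | week 13 | *v* weeks before the end (4 weeks before if *v* = 4 is assumed) |
| End of all intervention | week *v* + 26 | 13 weeks after |

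The third reading sits badly with the statement that the arms are compared by the end of implementing the education. On the first two readings the non-conventional arm has no reinforcement-free interval, while the conventional arm's single contact is about 3 months old.

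**The case against.** The strongest reply is that this is a legitimate comparison of packages. The hypothesis mentions conventional programmes, each arm is set out as a package, and nothing in the aim or objectives says that interactivity will be isolated or contact equalised. Repetition may be a deliberate ingredient. This stands as a defence of the design: the question of which programme does better is answerable. It does not rescue the framing, because neither the aim nor the hypotheses mention the difference in amount, and the rationale speaks for method.

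A reader might infer three stronger points, which the document does not support.

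- *That the trial contradicts itself on durability.* The Introduction does say "The efficacy of oral health education in schools is based on the extent to which the acquired health behaviors are retained", but that is cited background. No aim, objective or hypothesis promises a retained or long-lasting effect, so the absence of a later measurement is a limit on interpretation and not an inconsistency.
- *That one arm receives about 16 times the dose.* The ratio counts a home game as equal to a school visit and counts planned contacts, not those that take place. It is not a ratio of contact time.
- *That the outcome definitely falls while reinforcement is running.* This is the most natural reading, but it depends on a starting point that the Protocol leaves open.

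**Conclusion.** The point holds as a matter of attribution. Format is completely confounded with number of contacts: 4:1 in school visits, and 16:1 to 17:1 in planned contacts if every home game is counted as one. As the arm descriptions are written, it is also confounded with a mothers' lecture, which bears directly on the mothers' knowledge, attitudes and practices. The share of any difference due to the interactive or game-based method cannot be estimated from this trial.

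The conclusion that format and amount cannot be separated rests only on the arm descriptions. It needs no assumption about uptake, session length or sample size. The timing statement assumes that the 3 months run from the first or last school visit.

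The comparison of the two programmes as wholes is unaffected. The matter should be put right because the hypotheses are fixed in the Protocol and will shape the conclusion, and because only wording is needed.

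**What to change.** 1. Reconcile the section on who delivers the programme with the two arm descriptions, so that it is clear which mothers are offered the lecture.
2. Reconcile the game period, the Measurements section and the statement on when the arms are compared, and state the starting point of the 3 months and where the examination falls relative to the end of weekly play.
3. Restate the aim, hypothesis and null hypothesis as a comparison of two programmes as delivered. Each should be described by its components: number of school visits, weekly home play and its duration, any mothers' lecture as settled in item 1, and the assessment point as settled in item 2.
4. State in advance that a positive result will be attributed to the whole programme and not to the interactive format alone. If the outcome is confirmed to fall during or at the end of weekly play, say also that it will not be described as a retained effect.

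Neither programme has to change for this, nor does the sample size or the analysis. The cost is a narrower claim: that one programme did better than the other, not that one way of teaching did.
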